### **6.1.5 Early Termination Visit (All ARMS)**

To be completed within 7 days for subjects who do not proceed to Radical Prostatectomy.

- Physical examination
- Vital signs including blood pressure, heart rate, respiratory rate, temperature, pulse oximetry
- ECOG Performance status
- Evaluation of adverse events
- Concomitant medications
- CBC with differential and platelet count
- Blood chemistry assessment, including: Alkaline phosphatase, ALT/AST, total bilirubin, calcium, phosphorus, BUN, creatinine, total protein, albumin, fasting glucose, potassium, sodium, chloride, carbon dioxide, lipase, amylase
- PSA
- Immune monitoring

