Study Drugs	
PROSTVAC (Bavarian-Nordic) is a therapeutic cancer vaccine. Two component viral vectors (PROSTVAC-V, a recombinant vaccinia vector, and PROSTVAC-F, a recombinant fowlpox vector) are used together in a prime-boost vaccination regimen. Both vectors co-express a human PSA gene and genes encoding three human immunological costimulatory molecules: B7.1, intercellular adhesion molecule-1 (ICAM-1), and leukocyte function-associated antigen-3 (LFA-3).
 
Ipilimumab (Yervoy, Bristol-Myers Squibb) is a human immunoglobulin G-1 kappa monoclonal antibody that targets cytotoxic T lymphocyte-associated antigen-4 (CTLA-4). Ipilimumab was the first in a class of therapies targeting T cell activation and regulation to be licensed in the broad category of agents known as immune checkpoint inhibitors, based on improved overall survival in patients with metastatic melanoma.

Safety Assessments	Safety will be assessed by reviewing adverse events (AEs), laboratory evaluations, and by physical examination. The NCI CTCAE v4.03 will be used. All AEs and serious AEs (SAEs), with the exception of those considered related to RP, will be recorded on case report forms (CRFs) from enrollment through 12 weeks post-surgery
Efficacy Assessments	For the primary endpoint, the change in the number of CD3+ T cell infiltration within prostate tissue between the biopsy and RP specimen will be quantified using immunohistochemistry (IHC), with a positive result if there is $\geq 2$ fold increase in the number of CD3+ T cell infiltration.  As secondary endpoints we will look at changes in T cell subsets by IHC in the tissue and circulating T cells by flow cytometry. We will assess the toxicities according to NCI CTCAE v.4.03
Unique Aspects of this Study	This is the first study to: 1) evaluate the safety of systemic PROSTVAC or ipilimumab monotherapy, or the combination of PROSTVAC and ipilimumab, in the neoadjuvant setting in prostate cancer patients; 2) evaluate their direct effect both systemically, and in the tumor microenvironment. The secondary and exploratory studies will enhance the understanding of the immune effects of these therapeutic modalities.

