**Phase III trial of ipilimumab (10 mg/kg) and radiation versus radiation alone in the postdocetaxel setting (NCT00861614, Gerritsen, ESMO 2013) (28).** The study's primary endpoint of OS did not reach statistical significance with median OS at 11.2 months with ipilimumab (n=399) and 10 months with the placebo (n= 400; HR=0.85; 95 % confidence interval [CI]=0.72-1.00; p=0.053). Median progression-free survival favored ipilimumab over placebo (HR=0.7; 95 % CI=0.61-0.82) as did prostate-specific antigen (PSA) response rates, as evidenced by declines of  $\geq 50\%$  in evaluable patients (13.1 % vs. 5.3 %, respectively). Respective 1- and 2-year OS rates for ipilimumab vs placebo were 47% vs 40% and 26% vs 15%. Median PFS also favored ipilimumab over placebo (HR=0.70; 95%CI=0.61–0.82), as did PSA declines of  $\geq 50\%$  in evaluable patients (13.1% vs 5.3%, respectively). Pre-specified subset analyses suggest that ipilimumab may be most active in patients with no visceral disease and favorable laboratory prognostic factors (eg. decreased alkaline phosphatase, elevated hemoglobin). A post hoc analysis in patients who received treatment (n=779; n=387 for ipilimumab vs n=392 for placebo) showed an improvement in OS which favored ipilimumab (HR=0.84; 95%CI=0.71–1.00; p=0.0498). Treatment-related adverse events (AEs) were common and mostly immune-related AEs (irAEs). Grade  $\geq 3$  irAEs in the ipi vs pbo arms, respectively, were GI (18% vs 1%), liver (5% vs 1%), endocrine (2% vs 1%) and dermatologic (1% vs 0%); most were reversible using standard ipi management algorithms. Incidences of drug-related death and GI perforation were 1% and 0.6%, respectively.

A second phase III study that compares ipilimumab versus placebo in individuals with metastatic CRPC who have not already been treated with chemotherapy is ongoing (NCT01057810).

Combining cancer vaccines and ipilimumab would presumably improve anti-tumor activity by amplifying immune responses focused to relevant antigens as demonstrated in mice.

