
### 1.3.4 Safety: Ipilimumab at 3 mg/kg

The majority of data for drug-related AEs come from the studies with metastatic melanoma patients, where four doses of ipilimumab was the treatment schema. The most common treatment-emergent adverse events (AEs) considered by the investigator to be related to study drug in the metastatic melanoma trial (18) were irAEs, which occurred in approximately 60% of the patients treated with ipilimumab. The frequency of grade 3-4 immune-related adverse events was 10 to 15%. All irAEs occurred during the induction period (within the initial 4 doses). The irAEs most often affected the skin and gastrointestinal tract. The median time to the resolution of irAEs of grade 2, 3, or 4 was 4.9 weeks (95% CI, 3.1 to 6.4). The most common irAE was diarrhea, which occurred at any grade in 27 to 31% of the patients in the ipilimumab treated patients. After the administration of corticosteroids, the median time to the resolution of diarrhea of grade 2 or higher was 2.3 weeks for 14 of 15 patients. In addition to corticosteroids, 4 patients received

infliximab (anti-tumor necrosis factor  $\alpha$  antibody) for diarrhea of grade 3 or higher or colitis. Among the 94 persons who survived for 2 years, residual effects of AEs included those related to injection site reactions (16 patients), vitiligo (12), diarrhea or colitis (e.g., proctocolitis with rectal pain) (4), and endocrine irAEs (e.g., inflammation of the pituitary) that required hormone-replacement therapy (8). Ongoing events in the persons who survived for 2 years included rash pruritus, diarrhea, anorexia, and fatigue, generally of grade 1 or 2 (in 5 to 15% of the patients) and grade 3 leukocytosis (in one patient). There were 14 deaths related to the study drugs (2.1%), of which 7 were associated with immune-related adverse events.

In another study of metastatic melanoma patients comparing three different doses of ipilimumab (20), irAEs of any grade arose in 50 of 71, 46 of 71, and 19 of 72 patients at doses of 10 mg/kg, 3 mg/kg, and 0.3 mg/kg, respectively; the most common grade 3-4 adverse events were gastrointestinal irAEs (11 in the 10 mg/kg group, two in the 3 mg/kg group, none in the 0.3 mg/kg group) and diarrhea (ten in the 10 mg/kg group, one in the 3 mg/kg group, none in the 0.3 mg/kg group). Overall, grade 3-4 toxicities were seen in 25.4%, 7 % and 0%, respectively.

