### **6.1.6 Follow-up Study Procedures: (ALL ARMS, 9 weeks following RP (+/- 7 days))**

- Physical examination
- Vital signs including blood pressure, heart rate, respiratory rate, temperature, pulse oximetry
- ECOG Performance status

- Evaluation of adverse events
- Concomitant medications
- CBC with differential and platelet count
- Blood chemistry assessment, including: Alkaline phosphatase, ALT/AST, total bilirubin, calcium, phosphorus, BUN, creatinine, total protein, albumin, fasting glucose, potassium, sodium, chloride, carbon dioxide, lipase, amylase
- PSA
- Immune monitoring

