#### **6.1.7 Post-treatment/Follow Up Visits (ALL ARMS, 6 and 12 months following RP (+/- 7 days))**

Patients will be followed 6 and 12 months following RP, or until disease progression (whichever occurs first). The following procedures will be performed at the Follow Up Visit(s):

- Physical examination
- Vital signs including blood pressure, heart rate, respiratory rate, temperature, pulse oximetry
- Documentation of disease assessment
- ECOG Performance status
- Evaluation of adverse events
- Concomitant medications
- CBC with differential and platelet count
- Blood chemistry assessment, including: Alkaline phosphatase, ALT/AST, total bilirubin, calcium, phosphorus, BUN, creatinine, total protein, albumin, fasting glucose, potassium, sodium, chloride, LDH, carbon dioxide, lipase, amylase
- PSA
- Immune monitoring

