**Table 3 Schedule of Study Procedures and Assessments (ARMS A&C)**

Study Day/Visit Day	Screening Day -28 to 0	Day 1	Day 15 (± 3 days)	Day 36 (±3 days)	Day 57 f (± 7 days)	Early Termination e	9 wks post RP (± 7 days)		6 months post RP (± 7 days)	12 months post-RP (±7 days)
Informed consent	X									
Baseline conditions	X									
AE assessment		X	X	X	X		X	X	X	X
Concomitant medications	X	X	X	X	X		X	X	X	X
Obtain diagnostic biopsy or prostatectomy tissue	X				X					
Treatment/Drug Administration										
PROSTVAC – V (Arms A&C)		X								
PROSTVAC – F (Arms A&C)			X	X						
IPILIMUMAB (Arm C only)			X	X						
Clinical procedures										
Physical exam	X	X	X	X	X		X	X	X	X
Vital signs d	X	X	X	X	X		X	X	X	X
Medical history	X									
Disease assessment	X								X	X
Performance status	X	X a	X	X	X		X	X	X	X
IPSS	X				X					
ECG	X									

Study Day/Visit Day	Screening Day -28 to 0	Day 1	Day 15 (± 3 days)	Day 36 (±3 days)	Day 57 f (± 7 days)	Early Termination e	9 wks post RP		6 months post RP (± 7 days)	12 months post-RP (±7 days)
Laboratory procedures										
CBC w/ Diff b	X	X a	X	X	X	RP	X	X		X
Blood chemistry b	X	X a	X	X	X		X	X	X	X
Thyroid Function Tests	X		X	X	X					
PSA	X				X		X	X	X	X
Hepatitis B, C and HIV	X									
Urinalysis	X									
HLA Typing	X									
Immune Monitoring c	X		X	X	X		X	X	X	X

a Pre-study clinical (physical exam and performance status) and laboratory parameters are to be measured within 14 days of beginning treatment and do not need to be repeated on Day 1.

b CBC with differential and platelet count will be collected prior to study drug(s) dosing. Blood chemistry assessment, including: Alkaline phosphatase, ALT/AST, total bilirubin, calcium, phosphorus, BUN, creatinine, total protein, albumin, fasting glucose, potassium, sodium, chloride, LDH, carbon dioxide, lipase, amylase

c Refer to Laboratory Manual for collection procedures.

d Vitals that are to be taken at screening and at every provider visit prior to study drug administration are Blood pressure (diastolic & systolic), Heart Rate, Temperature, Respiration, & Pulse Oximetry. Weight is to be measured at screening and prior to Ipilimumab administration. Height is only required at screening. See Section 6.1.2 for Vitals schedule before and after study drug administration.

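### No TSH/T4 is scheduled at Early Termination, so an ipilimumab-treated man who never reaches surgery has no scheduled thyroid test after dose 2 (low priority, cheap to fix)

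*Combined protocol and SAP*

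**What the plan says.** The visit lists in Section 6.1 schedule TSH and T4 at screening, at Days 15 and 36 in Arms A and C, at Day 22 in Arm B, and among the pre-operative laboratory tests (Section 6.1.4: Day 57 in Arms A and C, Day 43 in Arm B, each +/- 7 days). The tests on dosing days stand among the assessments made before study drug is given.

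Men who do not have the operation go instead to the Early Termination visit of Section 6.1.5: "To be completed within 7 days for subjects who do not proceed to Radical Prostatectomy". It includes examination, adverse event review, blood count, chemistry, PSA and immune monitoring, but no thyroid test. The 9-week list in Section 6.1.6 is similar. Its chemistry panel ends with "fasting glucose, potassium, sodium, chloride, carbon dioxide, lipase, amylase" and it too has no thyroid test, nor has the list for 6 and 12 months in Section 6.1.7. The "Thyroid Function Tests" rows of Tables 3 and 4 agree with the lists.

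Section 5.6.5 counts endocrine events among the most common immune-related events. Section 5.6.1 asks for clinical monitoring of autoimmunity at each physician visit on the Appendix 3 form, which has spaces for TSH and T4.

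**The concern.** The protocol chose routine thyroid testing rather than waiting for symptoms, but the routine stops for the men who leave before surgery. They are the men for whom the pre-operative test, the only one after dose 2, does not happen. Some of them may be leaving because of toxicity.

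Safety is a secondary objective, and Section 7.3.1 allows an abnormal laboratory finding to count as an adverse event. Endocrine effects can also last. The phase I trial of ipilimumab with PROSTVAC (Section 1.3.3) reports indefinite hormone replacement, with two patients weaned off. The melanoma trial in Section 1.3.4 reports 8 endocrine events needing replacement among 94 two-year survivors. Without a scheduled exit test, finding a thyroid abnormality in these men depends on someone suspecting it.

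**Working it through.** **1. Which test follows which dose.** Dosing days are from Table 2 and test days from Sections 6.1.2 to 6.1.4.

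| | Arm B | Arm C |
|---|---|---|
| Ipilimumab dose 1 | Day 1 | Day 15 |
| Ipilimumab dose 2 | Day 22 | Day 36 |
| TSH/T4 after dose 1, before dose 2 | Day 22: 22 - 1 = 21 days | Day 36: 36 - 15 = 21 days |
| TSH/T4 after dose 2 | Day 43, pre-operative: 43 - 22 = 21 days | Day 57, pre-operative: 57 - 36 = 21 days |

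With surgery allowed +/- 7 days, the last test falls 14 to 28 days after dose 2. The Arm C test on Day 15 precedes the first ipilimumab dose, so it is a baseline value.

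**2. What each kind of patient gets.**

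- Reaches surgery, whatever doses he missed: one test after the last dose. Sections 3.4 and 5.2 keep him on study, and Section 6.1.4 tests him pre-operatively.
- Dose 1 only, attends the dose-2 visit, no surgery: one test after his last dose.
- Dose 1 only, leaves before the dose-2 visit, no surgery: none after exposure.
- Both doses, no surgery: none after dose 2.

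The gap consists of the last two groups.

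**3. How many men.** Section 8.2 accrues 42 for 13 evaluable in each of 3 arms: 42 - 3 x 13 = 3 planned dropouts, and 3/42 = 7.1%, matching the stated 7%. Arms B and C hold 2 x 14 = 28 men, and 28 x 0.07 = 1.96, so about 2. The arm of each dropout is unknown, so the range is 0 to 3. This assumes that every dropout fails to reach surgery and falls in one of the two uncovered groups, which puts it near a ceiling.

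**4. What an exit test could see.** Section 1.3.2 says immune-related events typically began no earlier than 3 to 4 weeks into therapy, that is 21 to 28 days. Take the 7 days of Section 6.1.5 to run from the decision to stop.

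- An Arm B man who stops on Day 4 is tested by Day 11, which is 11 - 1 = 10 days after first exposure and before that period.
- A man who stops on Day 25 is tested by Day 32. This is 32 - 1 = 31 days after dose 1 but only 32 - 22 = 10 days after dose 2.

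The test is therefore more informative after dose 2 than for a very early leaver.

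**5. Scale of yield.** The documents give three rough endocrine rates:

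- 2% at grade 3 or above, against 1% on placebo (Section 1.3.3, phase III trial at 10 mg/kg).
- 8/94 = 8.5% (Section 1.3.4, two-year survivors).
- 2/16 = 12.5% grade 2 hypophysitis (Section 1.3.3, 3 mg/kg with GVAX; exact 95% interval 1.6% to 38.3%).

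Applied to 2 men: 2 x 0.02 = 0.04, 2 x 0.085 = 0.17 and 2 x 0.125 = 0.25 expected cases. These rates cover endocrine events of several kinds at any time, under other doses, schedules or combinations. They show order of magnitude only, and they could be too low for men who stop because of toxicity.

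**6. Operated men, a separate matter.** Their last test is 21 + 21 = 42 days after dose 1. The 9-week visit is 9 x 7 = 63 days after surgery, so 42 + 63 = 105 days after dose 1 (91 to 119 with both windows) and 105 - 21 = 84 days after dose 2 (70 to 98).

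**The case against.** The strongest reply is that Appendix 3 already covers this. The form is due at each physician visit and lists TSH and T4. It limits stool analysis to patients with gastrointestinal symptoms but puts no such condition on the thyroid fields. Read strictly, it could prompt a test at exit. But the form also has fields for T3, FTI, ANA and RF, which no visit schedules, so it cannot be relied on as an order, and Section 6.1.5 does not refer to it. At best the form and the schedule disagree.

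Other safeguards exist: examination, adverse event review and chemistry at the exit visit, work-up of a suspected event (Section 5.6.5), and follow-up of men removed for treatment-related events (Section 3.5). These stand, but the last two need prior suspicion or a recognised event.

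It is also fair to say that the numbers are small, that the 7% in Section 8.2 is not defined as failure to reach surgery, and that a man who withdraws consent may not attend the exit visit. Section 1.3.3 says endocrine events were more common at 5 and 10 mg/kg than at the lower doses, Table 1 lists none at 3 mg/kg, and Section 1.3.4 warns that earlier data may not apply to two doses. All of this stands and keeps the priority low.

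**Conclusion.** The omission is real, and the visit lists show it without help from the tables. An ipilimumab-treated man who does not reach surgery has no scheduled thyroid test after dose 2, or none after exposure if he leaves before the dose-2 visit. At the planned dropout this is about 2 men, range 0 to 3, on the assumptions in the working. The primary analysis requires prostatectomy (Section 8.5.1), so these men are outside it already. The sample size is unaffected, and Section 8.7 plans no testing of adverse events.

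Three stronger readings are not supported.

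- A reader might take the missing 9-week test as part of the same gap. That visit is counted from surgery, so it cannot affect men who never had it.
- A reader might infer that an exit test would ensure detection. It ensures only that attendees have a scheduled test, which may precede onset.
- Adverse events are recorded "from enrollment through 12 weeks post-surgery", so a reader might see 12 x 7 = 84 days of unmonitored risk in operated men. That is calendar time, not risk time. The last test already falls about 42 days after dose 1, and the documents do not give the share of thyroid events that begin later.

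**What to change.** Add *TSH and T4 (ipilimumab-treated subjects, Arms B and C)* to Section 6.1.5. Mark the Early Termination cell of the thyroid row in Table 4 and, for Arm C only, in Table 3. State in Appendix 3 that its laboratory fields are completed where scheduled or clinically indicated. This is the change worth making. It costs about 2 assays (0 to 3) at a visit where blood is already drawn.

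Optionally, and with lower priority, add the same test for Arms B and C at the 9-week visit in Section 6.1.6. It could find a persisting abnormality. Each man has either the exit visit or the 9-week visit, so the two changes together add at most one assay per man: about 26 + 2 = 28. No new visit is needed; the documents do not say whether an extra tube would be. The downside is laboratory cost and occasional repeat tests for minor abnormalities.

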### **6.1.6 Follow-up Study Procedures: (ALL ARMS, 9 weeks following RP (+/- 7 days))**

- Physical examination
- Vital signs including blood pressure, heart rate, respiratory rate, temperature, pulse oximetry
- ECOG Performance status

- Evaluation of adverse events
- Concomitant medications
- CBC with differential and platelet count
- Blood chemistry assessment, including: Alkaline phosphatase, ALT/AST, total bilirubin, calcium, phosphorus, BUN, creatinine, total protein, albumin, fasting glucose, potassium, sodium, chloride, carbon dioxide, lipase, amylase
- PSA
- Immune monitoring

#### **6.1.7 Post-treatment/Follow Up Visits (ALL ARMS, 6 and 12 months following RP (+/- 7 days))**

Patients will be followed 6 and 12 months following RP, or until disease progression (whichever occurs first). The following procedures will be performed at the Follow Up Visit(s):

- Physical examination
- Vital signs including blood pressure, heart rate, respiratory rate, temperature, pulse oximetry
- Documentation of disease assessment
- ECOG Performance status
- Evaluation of adverse events
- Concomitant medications
- CBC with differential and platelet count
- Blood chemistry assessment, including: Alkaline phosphatase, ALT/AST, total bilirubin, calcium, phosphorus, BUN, creatinine, total protein, albumin, fasting glucose, potassium, sodium, chloride, LDH, carbon dioxide, lipase, amylase
- PSA
- Immune monitoring

#### **6.1.8 Discontinuation of Therapy**

The Investigator will withdraw a patient whenever continued participation is no longer in the patient's best interests. Reasons for withdrawing a patient include, but are not limited to, disease progression, the occurrence of an adverse event or a concurrent illness, a patient's request to end participation, a patient's non-compliance or simply significant uncertainty on the part of the Investigator that continued participation is prudent. There may also be administrative reasons to terminate participation, such as concern about a patient's compliance with the prescribed treatment regimen.

**Table 3 Schedule of Study Procedures and Assessments (ARMS A&C)**

Study Day/Visit Day	Screening Day -28 to 0	Day 1	Day 15 (± 3 days)	Day 36 (±3 days)	Day 57 f (± 7 days)	Early Termination e	9 wks post RP (± 7 days)		6 months post RP (± 7 days)	12 months post-RP (±7 days)
Informed consent	X									
Baseline conditions	X									
AE assessment		X	X	X	X		X	X	X	X
Concomitant medications	X	X	X	X	X		X	X	X	X
Obtain diagnostic biopsy or prostatectomy tissue	X				X					
Treatment/Drug Administration										
PROSTVAC – V (Arms A&C)		X								
PROSTVAC – F (Arms A&C)			X	X						
IPILIMUMAB (Arm C only)			X	X						
Clinical procedures										
Physical exam	X	X	X	X	X		X	X	X	X
Vital signs d	X	X	X	X	X		X	X	X	X
Medical history	X									
Disease assessment	X								X	X
Performance status	X	X a	X	X	X		X	X	X	X
IPSS	X				X					
ECG	X									

Study Day/Visit Day	Screening Day -28 to 0	Day 1	Day 15 (± 3 days)	Day 36 (±3 days)	Day 57 f (± 7 days)	Early Termination e	9 wks post RP		6 months post RP (± 7 days)	12 months post-RP (±7 days)
Laboratory procedures										
CBC w/ Diff b	X	X a	X	X	X	RP	X	X		X
Blood chemistry b	X	X a	X	X	X		X	X	X	X
Thyroid Function Tests	X		X	X	X					
PSA	X				X		X	X	X	X
Hepatitis B, C and HIV	X									
Urinalysis	X									
HLA Typing	X									
Immune Monitoring c	X		X	X	X		X	X	X	X

a Pre-study clinical (physical exam and performance status) and laboratory parameters are to be measured within 14 days of beginning treatment and do not need to be repeated on Day 1.

b CBC with differential and platelet count will be collected prior to study drug(s) dosing. Blood chemistry assessment, including: Alkaline phosphatase, ALT/AST, total bilirubin, calcium, phosphorus, BUN, creatinine, total protein, albumin, fasting glucose, potassium, sodium, chloride, LDH, carbon dioxide, lipase, amylase

c Refer to Laboratory Manual for collection procedures.

d Vitals that are to be taken at screening and at every provider visit prior to study drug administration are Blood pressure (diastolic & systolic), Heart Rate, Temperature, Respiration, & Pulse Oximetry. Weight is to be measured at screening and prior to Ipilimumab administration. Height is only required at screening. See Section 6.1.2 for Vitals schedule before and after study drug administration.

e Early termination visits are to be completed within 7 days for subjects who do not proceed to Radical Prostatectomy.

f Subjects will have routine postoperative follow-up assessments 10-42 days following RP as per urologic oncologist's discretion. Concomitant medications, adverse events, and ECOG performance status should be evaluated.

